## 4 Change to protocol specified analyses

NA.

## 5 Appendix

### 5.1 Imputation rules

#### 5.1.1 Study drug

The study drug administration date should be complete since it's taken in the hospital. In case missing or partial, the visit date will be used as the study drug administration date.

#### 5.1.2 AE date imputation

The following missing dates will not be imputed

- Missing AE start dates
- AE start dates missing the year
- Partial/missing AE end dates

For other type of missing dates, rules specified in [Tables 5-1](#) to [5-3](#) will be used

**Table 5-1 AE/Treatment Date Abbreviations**

	Day	Month	Year
Partial Adverse Event Start Date	<not used>	AEM	AEY
Treatment Start Date (TRTSTD)	<not used>	TRTM	TRTY

[Table 5-2](#) describes the possible combinations and their associated imputations. The upper text indicates the imputation (NC, A, B, C etc.) and the lower text the relationship of the AE start date to the treatment start date (TRTSTD).

**Table 5-2 Imputation algorithm**

	AEM MISSING	AEM < TRTM	AEM = TRTM	AEM > TRTM
--	-------------	------------	------------	------------

	AEM MISSING	AEM < TRTM	AEM = TRTM	AEM > TRTM
AEY MISSING	NC Uncertain	NC Uncertain	NC Uncertain	NC Uncertain
AEY < TRTY	( D ) Before TRTSTD	( C ) Before TRTSTD	( C ) Before TRTSTD	( C ) Before TRTSTD
AEY = TRTY	( B ) Uncertain	( C ) Before TRTSTD	( B ) Uncertain	( A ) After TRTSTD
AEY > TRTY	( E ) After TRTSTD	( A ) After TRTSTD	( A ) After TRTSTD	( A ) After TRTSTD

The legend to the above table is shown in [Table 5-3](#).

**Table 5-3 Imputation algorithm legends**

Relationship	
Before TRTSTD	Indicates AE start date prior to Treatment Start Date
After TRTSTD	Indicates AE start date after Treatment Start Date
Uncertain	Insufficient to determine the relationship of AE start date to Treatment Start Date
Imputation calculation	
NC / Blank	No convention/imputation
( A )	01MONYYYY
( B )	TRTSTD+1
( C )	15MONYYYY
( D )	01JULYYYY
( E )	01JANYYYY

Few examples are shown in [Table 5-4](#).

**Table 5-4 Example scenarios**

Partial AE start date	Treatment start date	Relationship with TRTSTD	Imputation Calculation	Imputed Date
12mmyyyy	20OCT2001	Uncertain	NC	<blank>
ddmmm2000	20OCT2001	Before	( D )	01JUL2000
ddmmm2002	20OCT2001	After	( E )	01JAN2002
ddmmm2001	20OCT2001	Uncertain	( B )	21OCT2001
ddSEP2001	20OCT2001	Before	( C )	15SEP2001
ddOCT2001	20OCT2001	Uncertain	( B )	21OCT2001
ddNOV2001	20OCT2001	After	( A )	01NOV2001

### 5.1.3 Concomitant medication date imputation

Missing concomitant medication dates will be imputed similar as to AE dates.

### 5.1.3.1 Prior therapies date imputation

**Start date:** The same rule which is applied to the imputation of AE/concomitant medication start date will be used with the exception that: for scenario (B) the start date will be replaced by the randomization date -1.

**End date:**

- Imputed date = min (reference end date, DEC 31 of the year), if month and day are missing.
  - Imputed date = min (reference end date, last day of the Month), if day is missing.
- where reference end date will be randomization date.

If the end date is not missing and the imputed start date is after the end date, use the end date as the imputed start date. If both the start date and the end date are imputed and if the imputed start date is after the imputed end date, use the imputed end date as the imputation for the start date.

### 5.1.3.2 Post therapies date imputation

**Start date:**

- If Day is missing, then impute to the max (reference start date, first day of the month).
- Day and month are missing then impute to the max(reference start date, Jan 1)
- Reference start date will be last date of study treatment administration + 1.

**End date:** No imputation.

### 5.1.3.3 Other imputations

NA.

### 5.1.4 Visit windows

When visit windows are used, all visits will be re-aligned, i.e., they will be mapped into one of the visit windows. E.g., if the Day 4 visit of a patient is delayed and occurs on Day 7, say, it will be re-aligned to visit window Day 8. In the case of major deviations from the visit schedule, or due to unscheduled visits, several assessments of a patient may fall in a particular visit window (either scheduled or unscheduled). Statistical approaches to handle multiple assessments in a given visit window are specified below.

- Of note, patients are allowed to have gaps in visits. All data collected will be displayed in listings.
- Lower limit and upper limit of the Day 15 visit is set to be Day 14 and Day 16 respectively, according to the protocol visit schedule since this is the primary analysis timepoint.
- The following rules are used to determine the window for other visits post baseline:
  - “Lower limit” = “upper limit of prior applicable visit” + 1.
  - “Upper limit” = “target day of current visit” + integer part of (“target day of next applicable visit” – “target day of current visit”)/2 with the exception of Day 29

- No upper limit for Day 29 visit
- Upper limit of Day 11 is one day before the lower limit of Day 15

For assessments that are scheduled to be performed only once on a day, [Table 5-5](#) describes the analysis windows mapping to visits (not just scheduled visits) based on study days alone. For the assessments that may be performed on multiple timepoints on a day, [Table 5-6](#) describes the analysis windows mapping to visits based on study day and time. Repeat and/or unscheduled visits (which will be numbered in the database according to new NCDS standards) will be mapped for analysis purposes in the same way. If there are multiple measurements within an analysis window, the conventions defined in [Table 5-7](#) will be used to determine the appropriate measurement to be selected for analysis.

The mapped visits will be used in the by visit analyses. However, the listings will show the collected data regardless of used in the by visit analyses.

**Table 5-5 Analysis visit windows based on study days alone**

Analysis Visit	Target Day	Analysis window for assessment group		
		Vital signs/ Chemistry/ Hematology	Urinalysis	Pregnancy
Baseline	1	Up to Day 1	Up to Day 1	up to day 1
Day 2	2	Day 2	Day 2-3	NA
Day 3	3	Day 3	NA	NA
Day 4	4	Day 4	NA	NA
Day 5	5	Day 5 - 6	Days 4-13	NA
Day 8	8	Day 7 – 9	NA	NA
Day 11	11	Day 10 – 13	NA	NA
Day 15	15	Day 14 – 16	Day 14 – 16	NA
Day 22	22	Day 17 – 25	NA	NA
Day 29/End of study	29	Day 26 and above	Day 17 and above	Day 2 and above

**Table 5-6 Analysis visit windows based on study day and time**

Analysis Visit	Analysis timepoint	Analysis window for assessment group			
		Temperature/ Parasite count	ECG		PK
			KAE609	Coartem	
Baseline	0 hrs	up to 0 hrs	up to < 0 hrs	up to < 0 hrs	NA
Day 1	1 hrs	NA	NA	NA	>0 to 1.5 hrs
	2 hrs	>0 to 3 hrs	NA	NA	>1.5 to 3 hrs
	4 hrs	>3 to 6 hrs	>0 to 8 hrs	NA	>3 to 5 hrs
	6 hrs	NA	NA	>0 to 37 hrs	>5 to 7 hrs
	8 hrs	>6 to 10 hrs	NA	NA	>7to 10 hrs
	12 hrs	>10 to 18 hrs	>8 to 18 hrs	NA	>10 to 18 hrs
Day 2	24 hrs	>18 to 30 hrs	>18 to 38 hrs	NA	>18 to 38 hrs
	36 hrs	>30 to 42 hrs	NA	NA	NA
Day 3	48 hrs	>42 to 54 hrs	NA	NA	>38 to 49 hrs

	50 hrs	NA	NA	NA	>49 to 51 hrs
	52 hrs	NA	>38 to 56 hrs	NA	>51 to 54 hrs
	56 hrs	NA	NA	NA	>54 to 58 hrs
	60 hrs	>54 to 66 hrs	>56 to 66 hrs	NA	>58 to 64 hrs
	68 hrs	NA	NA	>37 hrs to Day13	>64 to 70 hrs
Day 4	72 hrs	>66 hrs to Day 4	>66 hrs to Day 16	NA	>70 hrs to Day 6
Day 5	NA	Day 5-6	NA	NA	NA
Day 8	NA	Day 7 – 9	NA	NA	Day 7 – 9
Day 11	NA	Day 10 – 13	NA	NA	NA
Day 15	NA	Day 14 – 16	NA	NA	NA
Day 22	NA	Day 17 – 25	NA	NA	NA
Day 29/end of study	NA	Day 26 and above	Day 17 and above	Day 14 and above	NA

**Table 5-7 Rules for flagging variables**

Timing of measurement	Type of data	Rule
Baseline	All data	The last measurement made prior to and including administration of the first dose of study treatment – note this may include measurements taken on the day of randomization. If a patient did not receive any dose of study treatment then the randomization date will be used.
Post-baseline efficacy	All data	The measurement closest to the target day/time will be used. In the event that two measurements are taken equally apart (e.g. 1 day before target date and 1 day after) the first one will be used.
Post-baseline safety	Summary visit information (e.g. lab, ECG, etc.)	The measurement closest to the target day/time will be used. In the event that two measurements are taken equally apart, the first one will be used.
Post-baseline safety	Notable abnormalities (e.g. lab, ECG, VS)	The most extreme measurement in the window will be used. Note this means a patient can have a notably high and notably low measurement within a window

## 5.2 Prohibited medications

**Table 5-8 Table of prohibited medications with respective ATC codes**

Prohibited medication	ATC code	Drug	Comments
Antimalarials other than the study drug and rescue medication (Coartem)	P01BA	Aminoquinolines	Have not included codes for plain arthemether and arthemether/lumefantrine combination
	P01BB	Biguanides	
	P01BC	Methanolquinolines	
	P01BD	Diaminopyrimidines	
	P01BE	Artemisinin and derivatives, plain	
	P01BX	Other antimalarials	
	P01BF02	artesunate and mefloquine	
	P01BF03	artesunate and amodiaquine	

	P01BF04	artesunate, sulphamethopyrazine and pyrimethamine	
	P01BF05	artemimol and piperazine	
	P01BF06	artesunate and pyronaridine	
	P01BE01	artemisinin	
	P01BE03	artesunate	
	P01BE04	artemotil	
	P01BE05	artemimol	
Herbal medication			Do not have codes for this generic class
CYP3A4 metabolism thus potent and moderate CYP3A inhibitors (such as HIV antivirals: e.g. ritonavir miscellaneous: e.g. clarithromycin, itraconazole, ketoconazole, grapefruit juice, verapamil, cimetidine)	J05AR	Antivirals for treatment of HIV infections, combinations	do not have code for entire class of CYP inhibitors so provided codes for examples provided in the protocol
clarithromycin, itraconazole, ketoconazole, grapefruit juice, verapamil, cimetidine	J01FA09	clarithromycin	
	J02AC02	itraconazole	
	D01AC08	ketoconazole	
	G01AF11	ketoconazole	
	J02AB02	Ketoconazole	
	C08DA01	verapamil	
	A02BA01	cimetidine	grapefruit juice: code not available
barbiturates, carbamazepine, phenytoin, rifampin, st.John's wort	N03AA	Barbiturates and derivatives	
	N03AF01	carbamazepine	
	N03AB02	phenytoin	
	J04AB02	rifampicin	st.John's wort code not available
Proton pump inhibitors: e.g. lansoprazole, omeprazole, anti-	A02BC	Proton pump inhibitors	
	N03	ANTIEPILEPTICS	
	N06AA09	amitriptyline	Indomethacin= Indometacin

epileptics: e.g. phenytoin, miscellaneous: e.g., amitriptyline, chloramphenicol, clomipramine, indomethacin, nelfinavir, progesterone, proguanil, propranolol, warfarin	D06AX02	chloramphenicol	
	D10AF03	chloramphenicol	
	G01AA05	chloramphenicol	
	J01BA01	chloramphenicol	
	S02AA01	chloramphenicol	
	S03AA08	chloramphenicol	
	N06AA04	clomipramine	
	C01EB03	indometacin	
	M01AB01	indometacin	
	M02AA23	indometacin	
	S01BC01	indometacin	
	J05AE04	nelfinavir	
	G03DA04	progesterone	
	P01BB01	proguanil	
	C07AA05	propranolol	
B01AA03	warfarin		
Acetaminophen	N02BE01	paracetamol	Paracetamol=acetaminophen code not available for the following: Amoxicillin-clavulanic acid (co- amoxiclav) , Flucanazole, Glyburide, Ecstasy (MDMA) , Phencyclidine, Labetolol, Hydrazine, Trazadone, Ephedra
Alpha-methyldopa	C02AB	Methyldopa	
Ephedra	C01BD01	amiodarone	
Amoxicillin-clavulanic acid	A06AB06	senna glycosides	
Amiodarone	M03CA01	dantrolene	
Senna	N07BB01	disulfiram	
Dantrolene	P03AA04	disulfiram	
Disulfiram	A11CA	Vitamin A, plain	
Vitamin A	N01AB01	halothane	
Glyburide	A14A	ANABOLIC STEROIDS	
Halothane	B01AB01	heparin	
Anabolic steroids	C05BA03	heparin	
Heparin	S01XA14	heparin	
Cocaine	N01BC01	cocaine	
HMG-Co A reductase inhibitors	R02AD03	cocaine	
	S01HA01	cocaine	
Isoniazid	S02DA02	cocaine	
Phencyclidine (PCP)	C10AA	HMG CoA reductase inhibitors	
Ketoconazole	J04AC01	isoniazid	
Labetolol	D01AC08	ketoconazole	

Carbon tetrachloride	G01AF11	ketoconazole
	J02AB02	ketoconazole
Nicotinic Acid Chloroform	C04AC01	nicotinic acid
	C10AD02	nicotinic acid
Nitrofurantoin	J01XE01	nitrofurantoin
NSAIDs	M01A	NSAID
Hydrazine	M01AA01	phenylbutazone
Phenylbutazone	N03AB02	phenytoin
Phenytoin	J05AE	Protease inhibitors
Protease inhibitors	A07AB	Sulfonamides
Sulfonamides	D06BA	Sulfonamides
Terbinafine	G01AE	Sulfonamides
Trazadone	S01AB	Sulfonamides
Troglitazone	D01AE15	terbinafine
(withdrawn)	D01BA02	terbinafine
Valproic Acid	A10BG01	troglitazone
Bosentan	N03AG01	valproic acid
Propylthiouracil	C02KX01	bosentan
	D05BB01	etretinate
	H03BA02	propylthiouracil
	N01AB02	chloroform
	N01AB05	trichloroethylene

The prohibited medications listed in [Table 5-8](#) is not an exhausted list. Concomitant medications not listed above will be manually checked and will be categorized as Prohibited medication or non-prohibited medication.

The final list with all prohibited medications that were determined by medical review before database lock can be found in the excel file 'Copy of CKAE609A2202\_possible\_prohibited medications.xlsx'.

Copy of  
CKAE609A2202\_poss

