5.1.2 Additional treatment

Antipyretic will be allowed for symptomatic management of fever (see [Section 5.5.7](#)). No other additional treatment beyond investigational drug and control drug are included in this trial. The control drug, Coartem, will be also provided as rescue medication ([Section 5.5.6](#)).

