5.5.7 Prior and concomitant medication

Prior medications are defined as drugs taken and stopped prior to first dose of study medication.

Concomitant medication is defined as any medication, other than the Investigational Medicinal Product (IMP), which is given at least once between the day of first dose of randomized study medication and the last day of study visit (including those which were started pre-baseline and continued into the treatment period), including prescription and over-the-counter medicines, and any traditional or herbal remedies.

Paracetamol as an antipyretic, and metopimazine for repeated vomiting (or if not available, any other antiemetic which is not known to prolong QT and/or cause torsade de pointes) will be allowed. If paracetamol or equivalent drug is given as an antipyretic up to 72 hours prior first dose, it has to be reported as prior medication

Metoclopramide is contraindicated from the period prior to first dose to Day 5 post-dose (120 hours).

Beta-lactam antibiotics can be given in case of a bacterial infection appearing after enrolment. All other antibiotics, new-quinolones included, should be avoided where possible.

The investigator must instruct the patient to notify the study site about any new medications he/she takes after the patient was enrolled into the study. All medications, procedures and significant non-drug therapies (including herbal therapy, physical therapy and blood transfusions) administered after the patient was enrolled into the study must be recorded in the concomitant medications eCRF.

Each concomitant drug must be individually assessed against all exclusion criteria/prohibited medication. If in doubt the investigator should contact the Novartis medical monitor before randomizing a patient or allowing a new medication to be started.

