5.5.8 Prohibited medication

Use of the following treatments is NOT allowed as per below recommendation in **KAE609 Cohorts**:

- Antimalarials other than the study drug and rescue medication (Coartem) are not permitted during the entire study period.
- Herbal medication should not have been taken within 1 week before the study treatment is given and should be avoided until the last study visit.
- Any other investigational treatment for the whole study duration.
- KAE609 undergoes CYP3A4 metabolism thus potent and moderate CYP3A inhibitors (such as HIV antivirals: e.g., ritonavir miscellaneous: e.g., clarithromycin, itraconazole, ketoconazole, grapefruit juice, verapamil, cimetidine) and inducers (such as HIV antivirals: e.g., efavirenz miscellaneous: e.g., barbiturates, carbamazepine, phenytoin, rifampin, St. John's wort) are not allowed up to 14 days before enrolment in the study or minimum 5 half-lives of the perpetrator drug (whichever is longer) administration and up to 7 days post administration.
- KAE609 is a potent inhibitor of CYP2C19 and can potentially increase the exposure of drugs which are a substrate of CYP2C19 by many folds (such as Proton pump inhibitors: e.g., lansoprazole, omeprazole, anti-epileptics: e.g., phenytoin, miscellaneous: e.g., amitriptyline, chloramphenicol, clomipramine, indomethacin, nelfinavir, progesterone (synthetic progestins used in hormonal contraceptives are not prohibited since they are metabolized by CYP3A4), proguanil, propranolol, warfarin). Therefore, these are prohibited for the treatment duration and 7 days after last dose.
- Drug known to cause QTc prolongation or known to be potentially hepatotoxic (see [Appendix 4](#)) are prohibited for the treatment duration and 7 days after last dose.

Apart from the above mentioned possible interactions in vitro data suggest KAE609 is inhibitor of CYP2B6, CYP2C9, CYP2A6, CYP1A2, CYP2D6, CYP2C8, and CYP3A4, however, assessment including SimCYP simulation suggests that potential change in the exposure of drug substrate of any of these would be less than two fold and unlikely to be of clinical significance. Nonetheless caution should be exercised such as staggering the dose of victim drug by ~12 hours from last dose of KAE609.

Use of the following treatments is NOT allowed as per below recommendation in **Coartem/Riamet Cohorts**:

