Coartem/Riamet prescribing information should be followed in general. Use of any prescription drugs (with particular attention to use of CYP3A4 inhibitors, e.g., erythromycin, ketoconazole, itraconazole, cimetidine or CYP3A4 inducers e.g., rifampin, phenobarbital etc. Also drugs metabolized by CYP2D6 like flecainide, metoprolol, imipramine, amitriptyline, clomipramine, neuroleptics and those that increase QTc interval like terfenadine, astemizole, cisapride) is prohibited during study and within four (4) weeks prior to dosing. Herbal supplements are also prohibited during study and within one week prior to dosing. Medication which may be required to treat adverse events can be administered considering the potential interaction. Administration of paracetamol (daily total dose not to exceed 3g) / acetaminophen is acceptable, but dose and time of administration must be documented in the Concomitant medications / significant non-drug therapies section of the eCRF.

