Acute Kidney Injury: Serum creatinine increase \geq 50% compared to baseline	Follow up within 24-48h if possible Consider study treatment discontinuation Consider patient hospitalization /specialized treatment
Urine Event	
New dipstick proteinuria \geq 1+ Albumin- or Protein-creatinine ratio increase \geq 2-fold Albumin-creatinine ratio (ACR) \geq 30 mg/g or \geq 3 mg/mmol; Protein-creatinine ratio (PCR) \geq 150 mg/g or $>$ 15 mg/mmol	Confirm value after 24-48h Perform urine microscopy Consider study treatment discontinuation
New dipstick glycosuria \geq 1+ not due to diabetes	Blood glucose (fasting) Perform serum creatinine
New dipstick hematuria \geq 1+ not due to trauma	Urine sediment microscopy Perform serum creatinine
For all renal events:	

Document contributing factors in the CRF: co-medication, other co-morbid conditions, and additional diagnostic procedures performed
 
Monitor patient regularly (frequency at investigator's discretion) until either:
 
Event resolution: sCr within 10% of baseline or protein-creatinine ratio within 50% of baseline, or
 
Event stabilization: sCr level with \pm 10% variability over last 6 months or protein-creatinine ratio stabilization at a new level with \pm 50% variability over last 6 months.
 
sCr: serum creatinine.
	

16 Appendix 4: Medications, herbs and toxins as cause of ALT/AST elevations

Table 16-1 Medications, herbs and toxins as cause of ALT/AST elevations

Medications and drugs	Herbs and alternative medications
Alpha-methyldopa	Chaparral leaf
Amoxicillin-clavulanic acid	Ephedra
Amiodarone	Gentian
Bosentan	Germander
Carbamazepine	Ji Bu Huan
Dantrolene	Senna
Disulfiram	Kava kava
Etretinate	Scutellaria (skullcap)
Fluconazole	Shark cartilage
Glyburide	Vitamin A
Halothane	Illicit drugs
Heparin	Anabolic steroids
HMG-Co A reductase inhibitors	Cocaine
Isoniazid	Ecstasy (MDMA)
Ketoconazole	Phencyclidine (PCP)
Labetalol	Toxins
Nicotinic Acid	Carbon tetrachloride
Nitrofurantoin	Chloroform
NSAIDs	Dimethylformamide
Phenylbutazone	Hydrazine
Phenytoin	Hydrochlorofluorocarbons
Propylthiouracil	2-Nitropropane
Protease inhibitors	Trichloroethylene
Sulfonamides	Toluene
Terbinafine	
Trazadone	
Troglitazone (withdrawn)	
Valproic Acid

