#### **2.4.2 Prior, concomitant and post therapies**

Prior and concomitant medications will be summarized in separate tables by cohort and treatment group.

Concomitant rescue and other anti-malarial medications will also be summarized by cohort and treatment group.

Note – The only rescue medication considered in this study is Coartem. All other antimalarial drugs are prohibited and if taken then it will be considered as PD. If Coartem is used after discontinuation of study drug due to early treatment failure, late clinical failure or late parasitological failure then it should be considered as rescue medication,. Rescue medication will be captured along with other concomitant medications by the investigators under rescue medication category.

Any patient on KAE609 who does not need rescue medication up to Study Day 28 will be given Coartem as post therapy at the end of the study (Study Day 29) and will be followed as per standard medical care. Prior medications are defined as drugs taken and stopped prior to first dose of study medication. Any medication given at least once between the day of first dose of study medication and the last day of study visit will be a concomitant medication, including those which were started pre-baseline and continued into the treatment period.

Prior and concomitant medications will be coded according to the latest version of WHO Drug Reference List dictionary which employs the ATC. The number and percentage of patients taking prior and concomitant medications will be summarized for each cohort and treatment by ATC class and preferred term (PT).

Number and percentage of the patients receiving prohibited prior and concomitant drugs will be summarized. Details regarding prohibited drugs are mentioned in [Table 5-9](#). PK related prohibited medications (the drugs which are prohibited only within first 7 days from first dose) and non-PK related prohibited medications will be summarized separately.

Safety set will be used.

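### SAP Table 5-8 codes paracetamol (N02BE01) as prohibited although the protocol allows it as an antipyretic, so the prohibited-medication summary could count allowed use

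*SAP*

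**What the plan says.** **SAP.** Section 5.2 lists prohibited medications with ATC codes in Table 5-8. One row reads acetaminophen, N02BE01, paracetamol. Its comment begins "Paracetamol=acetaminophen code not available for the following". This is two notes run together: a synonym note for paracetamol, then a note that other drugs (for example glyburide and labetalol) have no code. The evidence is the row and its code, not the comment.

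Below the table the SAP says: "Concomitant medications not listed above will be manually checked and will be categorized as Prohibited medication or non-prohibited medication". It then says that the final list was settled by medical review before database lock and is held in a spreadsheet.

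The list is used in SAP 2.4.2: "Number and percentage of the patients receiving prohibited prior and concomitant drugs will be summarized", on the Safety set. Table 2-4 plans both the prior and the concomitant summaries, with listings. SAP section 4 declares no change from the protocol's analyses.

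**Protocol.**
- Section 5.1.2: "Antipyretic will be allowed for symptomatic management of fever".
- Section 5.5.7 names among the allowed drugs "Paracetamol as an antipyretic, and metopimazine for repeated vomiting".
- Section 5.5.8, Coartem part: "Administration of paracetamol (daily total dose not to exceed 3g) / acetaminophen is acceptable".
- Section 5.5.8, KAE609 part, bars any "Drug known to cause QTc prolongation or known to be potentially hepatotoxic" during treatment and for 7 days afterwards, and refers to Appendix 4.
- Appendix 4 is "Table 16-1 Medications, herbs and toxins as cause of ALT/AST elevations". It begins at alpha-methyldopa and has no entry for paracetamol or acetaminophen.

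**The concern.** A drug that the protocol allows appears with a code on the SAP's list of prohibited drugs. A program that matches ATC codes to that list would report allowed antipyretic use as use of a prohibited drug.

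Paracetamol use is to be expected in this population. Every patient enters with fever or a history of fever in the previous 24 hours. Protocol 5.5.7 also requires paracetamol given up to 72 hours before the first dose to be reported as prior medication. Allowed use can therefore enter both the prior and the concomitant counts.

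At stake is whether one descriptive summary means what its title says. In a trial whose primary endpoint is a rise in ALT or AST, a reader will look at the prohibited-drug percentage to judge whether liver findings might have another cause. A percentage made up partly of an allowed antipyretic does not answer that question.

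**Working it through.** The plan gives no figure to reproduce. The check is a comparison of texts, followed by a simple illustration of size.

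**1. Is the drug allowed under the protocol?**

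| Place | Status of paracetamol | Condition |
|---|---|---|
| Protocol 5.1.2 | antipyretics allowed | for fever |
| Protocol 5.5.7 | allowed | as an antipyretic; not limited to one arm |
| Protocol 5.5.8, Coartem part | acceptable | daily maximum; dose and time recorded |
| Protocol 5.5.8, KAE609 part | not named | hepatotoxic drugs barred by reference to Appendix 4 |
| Protocol Table 16-1 | not listed | none |
| SAP Table 5-8 | listed as prohibited, N02BE01 | none |

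The other drug names in that block of Table 5-8 all appear in Table 16-1; acetaminophen is the one that does not. If a row of Table 16-1 had been lost in the copy available, the conflict between Table 5-8 and Protocol 5.5.7 would remain.

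**2. Does anything written remove the row before the summary is made?** The manual check covers medications that are not in Table 5-8. Paracetamol is in the table, so the check does not reach it. The reviewed final list might omit it, but the SAP does not say that the review can take out a listed drug, and the file cannot be seen.

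**3. What would the row do if applied literally?** Let N be the number of patients and u the share who take paracetamol. Patients flagged on paracetamol = N × u. The overall prohibited-drug percentage then cannot fall below u, whatever the use of the other listed drugs.

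N is about 210 (Protocol section 4). The documents do not give u, so a range is assumed:

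| Assumed u | 210 × u | Patients flagged |
|---|---|---|
| 25% | 52.5 | about 53 |
| 50% | 105 | 105 |
| 75% | 157.5 | about 158 |
| 90% | 189 | 189 |

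If N02BE01 is not counted, the number flagged on paracetamol alone is 0.

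**4. Does it reach any other analysis?**
- *Primary analysis (SAP 2.5.2):* it uses the Safety set. The Table 5-9 exclusions for that set are not being in the Randomized set and having taken no study drug. Prohibited medication plays no part.
- *Per-protocol and PK sets:* the prohibited-medication deviations in Table 5-9 (COMD01b, COMD01c) apply only where the drug was found to change exposure, with an effect on efficacy or on PK parameters. Being on the list does not by itself exclude a patient.

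**The case against.** The strongest reply is that Table 5-8 is not the operative list. The SAP calls it incomplete and points to a final list set by medical review. If that review left paracetamol out, the summary is already right and only the printed table is wrong. This stands as a limit on the conclusion: miscounting is possible but not established. It does not remove the conflict in the text, because the SAP gives no rule by which a listed drug is cleared.

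The protocol's permission is also conditional. Section 5.5.7 allows the drug as an antipyretic, and the daily maximum stands only in the Coartem part of 5.5.8. Deleting the code outright could lose a screen for use outside those conditions. This too stands, and is why paracetamol should keep a line of its own.

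A reader might infer two stronger things that the documents do not support:

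- *That most patients would be flagged.* This needs u above 50%. Fever at entry makes substantial use plausible, but no rate is given. A history of fever is enough for entry, and Protocol 9.5.1.3 foresees patients with no fever at pre-dose.
- *That real use of hepatotoxic or interacting drugs would be hidden.* SAP 2.4.2 also tabulates all prior and concomitant medications by ATC class and preferred term. Table 2-4 provides listings of prohibited medications, and the primary results are read together with patient narratives. A headline percentage could be inflated, but no drug-level information is lost.

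**Conclusion.** The conflict is real and limited. SAP Table 5-8 codes as prohibited a drug that Protocol 5.1.2 and 5.5.7 allow as an antipyretic and 5.5.8 accepts in the Coartem arms, and the SAP declares no departure. Taken literally, the table would put allowed use into the prohibited-drug summaries.

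The size rests on two unknowns: the paracetamol use rate, and whether the reviewed final list already leaves the drug out. Under an assumed use of 25% to 90%, about 53 to 189 of about 210 patients would be flagged; if the final list omits the drug, none would be. No estimate, confidence interval or test of the primary endpoint changes, and Table 5-9 excludes nobody on this ground alone. What remains is a wrong coding rule for one descriptive safety summary, worth correcting but minor.

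**What to change.** 1. Reconcile Table 5-8 with Protocol 5.1.2, 5.5.7, 5.5.8 and Table 16-1, so that paracetamol use the protocol allows is not counted as prohibited. This aligns the coding with the protocol's own text and proposes no clinical rule.
2. State in SAP 5.2 whether N02BE01 is on the reviewed final list, and confirm that the list and the program follow the same rule.
3. Show paracetamol use on a separate line by cohort and treatment group, so that use outside the protocol's stated conditions can still be reviewed.
4. In the same edit, correct the cross-reference in SAP 2.4.2, which sends the reader to Table 5-9 for prohibited drugs; the list is in Table 5-8.

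The cost is one table row, one code in the program, one line of output and one cross-reference. No new data are needed.
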